2.4 Inclusion and exclusion criteria

Inclusion criteria

- Able to provide signed and dated informed consent form
- Male or female, 19 to 99 years of age
- Persistent arterial hypertension with systolic blood pressure above 150 mmHg during hospitalisation and the day of randomisation
- Stable anti-hypertensive medication with at least two guideline-recommended anti-hypertensive drugs

Exclusion criteria

- Systolic blood pressure ≥180mmHg on the day of randomisation
- Spermidine intolerance
- Significant renal impairment defined as glomerular filtration rate < 45ml/min
- Insulin-dependent diabetes mellitus (IDDM)
- Wheat allergy or gluten intolerance
- Life expectancy of less than 12 months

- Participation in another clinical trial

2.5 Data management / documentation

Data will be collected on paper-based CRFs. CRFs will remain the property of the study center (Medical University of Graz). Data analysis will be performed using SPSS on the institutional computers of the investigators.

2.6 Sample size considerations

As outlined in 2 and 2.1., the blood pressure-lowering effect of spermidine is well established in animal models. Furthermore, 28 elderly patients with subjective declining cognitive function within the SMARTAGE trial revealed a drop in systolic blood pressure of 10 mmHg (4.5 mmHg more than in the placebo group) upon spermidine (1.2 mg/day) supplementation for three months. In the proposed trial, we will use a three-fold higher dose of spermidine and we will enroll patients with a higher baseline blood pressure (≥ 150 and ≤ 180 mmHg systolic BP). Therefore, we expect a reduction of systolic blood pressure of at least 5 mmHg. To this end, we calculated that a total of 38 patients would be sufficient to detect that effect at a power of 80%, assuming a two-tailed α value (type-I error) of 5%, blood pressure variance (SD) of 13 mmHg and within-subject correlation coefficient (r) of 0.65. We expect a drop-out rate of 15% due to the 20-week-long duration of the trial, thus, a total number of 46 patients will be enrolled.

2.7 Follow-up

Study follow-up will be twenty weeks, comprised of two treatment periods of eight weeks and a washout period of four weeks between both treatments.

2.8 Project duration and milestones

We envision that a period of 21 months will be needed to successfully accomplish this study. The recruitment (18 months) is planned as follows:

First patient visit:	February 2020
Last patient enrolled:	June 2021

3 Methods

3.1 24h BPM

During each of the four visits patients will be supplied with an ambulatory blood pressure measurement (ABPM) device (Mobil-O-Graph® PWA, I.E.M. GmbH, Stolberg, Germany). After 24 hours of continuous BPM at their homes, patients will remove the device and return it to the study center via postal service. Mobil-O-Graph® PWA is a well established device to measure central blood pressure and pulse wave velocity used and validated in multiple clinical trials and settings. Despite being a non-invasive technique good accuracy compared to intra-aortic readings has been proven (linear correlation $R=0.81$, $p < 0.0001$) in 120 patients (see validation data on www.iem.de/en/health-management/studies-validations.html and a bibliography at www.iem.de/files/content/DE/IEMintern/Support/Hintergründe/Bibliography%20Mobil-O-Graph%20Blood%20Pressure%20PWA%202.9.pdf) During the visit on-site blood pressure measurements and a standardized 6MWT will be conducted at every visit.

3.2 Lab analysis

Blood withdrawal will be performed using:

- 4x Lithium-heparinate: $8+7+2+2$ ml=19 ml blood
- 1x Serum: 4 ml blood for approx. 2 ml serum
- 1x EDTA: 7 ml blood for approx. 3.5 ml plasma

Blood draws will be performed at each of the four visits (total blood volume taken during the trial will be 120 ml).

In addition to standard clinical assessments (see 2.3.2), the isolation of PBMC will be performed from the whole blood samples and analysed to assess alterations in immune cell populations using state-of-the-art multi-parameter flow cytometry and/or Cy-TOF. In several multi-systemic pathologies, possibly rare, differentiated or non-differentiated hematopoietic cell subpopulations, which can be detected in circulation, have been increasingly recognized as a read-out to determine/distinguish between health and disease status. Advances in single cell-resolved molecular measurement technologies enabled the description of cell population heterogeneity, including rare disease-associated subpopulations. However, the identification of such subpopulations remains a difficult computational task. Therefore, our collaborator [name] (ETH Zurich, Switzerland) has developed²¹ an artificial intelligence approach that detects disease-associated subpopulations of cells from single-cell proteomic measurements using this CyTOF

techniques²². These data will be examined for correlations with systolic and diastolic blood pressures as well as with markers of inflammation employing flow cytometry-based assessment of cytokines. In addition, autophagic flux will be measured using LC3-lipidation quantification in *ex vivo* leupeptin-treated PBMCs²⁰) in human leukocytes. Altogether, this will allow us to describe, for the first time, *in vivo* effects of spermidine intervention on human immune cells, inflammatory cytokines, and markers of autophagy.

3.3 Electrocardiography

Conventional 12-lead ECG.

3.4 Echocardiography

Standardized 2D-echocardiography will be performed at every visit. Loops will be recorded and stored as outlined in the echo manual (parasternal long and short axis, 2-, 3- and 4-chamber view, subcostal view). For details, see the attached protocol for Echo-CRF.

3.5 QoL assessment

The standardized and well-established SF-36 questionnaire will be used to evaluate a subjective quality of life of the patients.

4 Safety and risk management

The planned daily dose of spermidine is an approved dietary supplement extracted from spermidine-rich wheat germ (see <http://eur-lex.europa.eu/legal-content/EN/TXT/PDF/?uri=CELEX:32017R2470&from=EN>). Additionally, spermidine is part of a standard healthy diet, present in a wide variety of foods. Therefore, the dose of 4 mg spermidine per day is unlikely to cause any harm to the patients participating in the study. The reduction in blood pressure would be a beneficial therapeutic effect considering the hypertensive baseline. However, a NO/arginine-mediated blood pressure-lowering effect may also cause headaches, dizziness or tachycardia. The study protocol does not interfere with standard baseline therapy. Upon study completion, patients will be invited to participate in the educational program “herz.leben” (ADD link to the webpage!) and, therefore also receive optimal lifestyle modification training.

4.1 Adverse events and reactions

Adverse Events (AE), Adverse Reactions (AR), Unexpected Adverse Reactions (UAR) as well as Serious Adverse Events (SAE), and Serious Adverse Reactions (SAR) will be recorded and reported to the institutional ethics committee as outlined in the ethics approval.

4.2 Study discontinuation

One or more of the following incidences would lead to a discontinuation of the study for a single patient (drop-out):

- Withdrawal of consent
- Intolerable investigational drug-related effects
- Severe violation of the study protocol
- New onset of an exclusion criterion during the treatment period
- Decrease in blood pressure of more than 40 mmHg with symptomatic hypotension

Early discontinuation of the study will be taken into a consideration if the risk-benefit relationship worsens:

- Intolerable investigational drug-related effects in more than 10 patients
- Decrease in blood pressure of more than 40 mmHg with symptomatic hypotension in more than 10 patients

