4.3 Potential risks within the study design

All clinical assessments in this trial are standard methods and well established within the Department of Cardiology (MedUniGraz) and its clinical trial section. Thus, the applicant does not expect any methodological risk with respect to the trial. The recruitment of patients into this clinical trial will be based on the cooperation between the applicant and the herz.leben project, in which 120 highly motivated patients per year have been prospectively enrolled since 2007. Therefore, we do not anticipate having problems with recruiting 42 patients from this educational program within 12 months and expect these patients to fully adhere to the study protocol.

Saliva collection by swabbing is a very convenient and non-invasive method for collecting cells in clinical practice. However, saliva samples might not contain enough cells to perform all analyses, including the assessment of autophagic activities. Therefore, whole blood and blood cells (e.g. PBMCs) will be used to detect differences in autophagy, immune cell, and polyamine metabolite profiles. We work under the hypothesis that spermidine induces autophagy in hypertensive patients. If we fail to detect increased autophagy markers upon spermidine supplement, we will use

our data on plasma metabolites (such as L-arginine) and any detected changes in circulatory cell profiles to propose an alternative mode of action (potentially autophagy-independent). If spermidine levels are not increased in whole blood or plasma, our efforts will concentrate on the detection of spermidine-induced changes in polyamine metabolism by analyzing metabolites (i.e. precursors and derivatives of spermidine) in human plasma samples. Moreover, saliva samples offer an additional “tissue”-like sample that will prove the bioavailability of spermidine originating from the administered supplements.

5 Statistical considerations and data analysis

Obtaining repeated measurements from the same patients in response to both treatments has fundamental physiological reasoning (see 3.1) and necessitates completing the study protocol. For this reason and because the trial is designed to measure the treatment efficacy, rather than adherence, patients who drop out before completing the protocol (4 visits) or their baseline treatment regimen changes due to medical reasons will be excluded to maintain a balanced crossover analysis of this trial.

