The effect of distinct treatments (spermidine or placebo) on a given parameter (e.g. SBP) will be expressed as a change score from baseline (Δ). The difference between treatment effects will then be evaluated using a mixed linear model, where *Subjects* will be included as a random factor, whereas Treatment (spermidine vs. placebo), *Period* (first vs. second), and *Sequence* (spermidine-placebo vs. placebo-spermidine) will be fixed factors (i.e. predictors). Although we expect no carryover effects due to the washout period, including *Period* and *Sequence* in the model will help exclude any confounding effects of (or interaction with) these aspects, especially taking into account that the obtained data will be well-balanced due to the (2x2) study design.

6 Ethical considerations and informed consent

The study shall be conducted in accordance with the ethical principles originating from the *Declaration of Helsinki*²³ and in accordance with *ICH-Good Clinical Practice* (GCP) and applicable regulatory requirements. The study is registered at the local ethics committee with the number 30-468 ex 17/18.

Before randomisation, patients will be comprehensively informed about spermidine and its effects as a compound and the procedures within the trial, but they will be blinded to the treatment sequence (spermidine vs. placebo). Participants will be given the informed consent form and given enough time to consider voluntary participation.

7 Data collection and quality assurance, Data management, Monitoring

A unique ID number will be attributed to every enrolled patient. Patients' names will be protected and accessible only to the personnel/the applicant involved in the study. Blood/serum samples will be stored in an anonymous fashion and biologically destroyed 5 years after completion of the study.

On-site monitoring will be conducted by the KKS (Koordinierungszentrum für Klinische Studien), MedUniGraz. Accuracy and completeness of the CRF entries, source documents, and other study-related documents will be checked. After each monitoring visit, a report of any significant findings/facts, deviations, and deficiencies will be communicated to the investigator.

Conflict of interest:

[name] and [name] declare a potential financial conflict of interest (equity in TLL). They will not analyze any clinical data and will be blinded throughout the lab analysis after the trial.

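### Section 4.2 makes product-related stops study drop-outs with no later measurement planned, and Section 5 then discards the data those patients already have

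*Combined protocol and SAP*

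**What the plan says.** Section 4.2 gives five events that "would lead to a discontinuation of the study for a single patient (drop-out". Withdrawal of consent is one. "Intolerable investigational drug-related effects" and "Decrease in blood pressure of more than 40 mmHg with symptomatic hypotension" stand beside it with the same consequence, as do a severe protocol violation and a new exclusion criterion. For the trial as a whole, early termination is only considered above a count, for example "Intolerable investigational drug-related effects in more than 10 patients".

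Table 1 (Section 2.2) places 24-hour blood pressure, laboratory tests, ECG, echocardiography and SF-36 at weeks 0, 8, 12 and 20 only. Section 2.7 states "Study follow-up will be twenty weeks". Neither describes an early-termination visit, or attendance after the product has been stopped.

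Section 5 says that "patients who drop out before completing the protocol (4 visits) or their baseline treatment regimen changes due to medical reasons will be excluded", on the ground that "the trial is designed to measure the treatment efficacy, rather than adherence". The outcome "will be expressed as a change score from baseline", so each treatment needs a value at the end of its own period. No method for missing data and no sensitivity analysis is given.

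**The concern.** Stopping a product and ending measurement are different decisions, and Section 4.2 joins them. Withdrawn consent ends both. After the two product-related events a patient may still be willing to be measured, but the plan has no provision for it.

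This has consequences that a later change of analysis set cannot repair. Section 5 could be supplemented by an analysis of all randomised patients, but a measurement that was never taken cannot be recovered. The reasons for the loss are also not neutral. One trigger is tolerance of the product and the other is a change in the variable that the trial measures. Section 4 itself expects that a pressure-lowering effect might bring headache, dizziness or tachycardia. Losses could therefore be more frequent on spermidine than on placebo and could depend on response. Patients with these events would also have no scheduled ECG, laboratory or on-site pressure check afterwards.

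**Working it through.** **1. What each stop leaves behind (Table 1 and Section 5).**

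| Product stopped in | Week 0 | Week 8 | Week 12 | Week 20 | Used under Section 5 |
|---|---|---|---|---|---|
| Period 1 (weeks 0–8) | yes | none planned | none planned | none planned | no |
| Period 2 (weeks 12–20) | yes | yes | yes | none planned | no: existing data removed |

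For a period-1 stop the loss comes from Section 4.2. For a period-2 stop the week-20 loss comes from Section 4.2, and the loss of the week-8 value comes from Section 5.

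**2. The plan's own sample size.** Inputs from Section 2.6: effect 5 mmHg, SD 13 mmHg, within-subject correlation 0.65, two-sided 5%, power 80%, drop-out 15%.
- SD of the within-patient difference = 13 × √(2 × (1 − 0.65)) = 10.88 mmHg.
- n = ((1.960 + 0.842) × 10.88 / 5)² = 37.1, rounded up to 38, as stated.
- 38 / (1 − 0.15) = 44.7, so 45, or 46 as an even number. The stated 46 is reproduced.
- Expected drop-outs: 46 × 0.15 = 6.9, about 7. Section 2.6 attributes them to trial length, not to tolerability or hypotension.

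**3. How often the pressure trigger might act.** No rate is given. Assume normally distributed changes with a mean fall of 5 to 10 mmHg and take 10.88 as the SD.
- Mean fall 5: (40 − 5) / 10.88 = 3.22, probability 0.06%, or 0.03 of 46 patients.
- Mean fall 10: (40 − 10) / 10.88 = 2.76, probability 0.29%, or 0.13 of 46 patients.

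These are upper bounds under those assumptions, because symptoms are also required. Section 4.2 does not say which reading or which reference value counts. With an assumed SD of 20, which is not in the documents, the figures are 4.0–6.7%, or 1.8–3.1 patients. On the plan's own SD and correlation, tolerability is the likelier route of loss.

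**4. Possible shift in the estimate.** If k of 46 patients are removed and their mean treatment difference lies D mmHg from that of the patients who remain, the shift is (k / 46) × D. Both k and D are assumptions; k = 7 would make every expected drop-out a product-related one.
- k = 3: 3/46 × 5 = 0.3; 3/46 × 10 = 0.7 mmHg.
- k = 7: 7/46 × 5 = 0.8; 7/46 × 10 = 1.5 mmHg.

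The range is 0.3 to 1.5 mmHg, or about 6% to 30% of 5 mmHg. If D is instead measured from the mean of all 46, the divisor becomes 46 − k and the range is 3/43 × 5 = 0.35 to 7/39 × 10 = 1.8 mmHg.

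**5. Does continued attendance raise power?** Start from 46 − 6.9 = 39.1 patients (power 79.9%, noncentral t, n − 2 degrees of freedom) and suppose 2, 3.5 or 5 more are measured. If they contribute no effect, the average effect becomes 5 × 39.1 / (39.1 + extra).

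| Extra patients | Power, full 5 mmHg | Power, half effect | Average effect and power, zero effect |
|---|---|---|---|
| 2 | 82% | 80% | 4.76 mmHg, 78% |
| 3.5 | 83% | 80% | 4.59 mmHg, 77% |
| 5 | 85% | 80% | 4.43 mmHg, 75% |

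Power can move either way, so it is not an argument for the change.

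**The case against.** The best defence is that the plan states its target: efficacy in patients who complete both treatments. For that question off-product values are not wanted. They would not supply the on-product response of a patient who stopped, and someone who stops early in a period could be off product for four weeks or more by its closing visit, as long as the plan's own washout. This stands, and it is why the completers analysis should remain. It does not explain why measurement should end, or why nothing is reported on everyone randomised.

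It can also be said that the documents do not forbid later visits. That is correct: their absence is inferred from the drop-out label and from silence elsewhere. Likewise, Section 4.1 has adverse events recorded and reported as the ethics approval sets out. That approval is not among the documents, and Section 4.1 does not confine reporting to completers. What is missing is a stated plan for the scheduled assessments, not adverse event reporting as such.

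Finally, Section 4 regards harm as unlikely, and Section 2.6 ties drop-out to duration. Product-related stops may be few. That limits the size of the problem, but the documents give no rate.

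**Conclusion.** The gap is real and moderate in weight. Product-related stops are classed as study drop-outs, no later measurement is planned, and Section 5 then removes what such patients already contributed. The loss depends on tolerance or response and may differ between treatments. The 0.3 to 1.5 mmHg shift rests wholly on the assumed 3 to 7 patients and the assumed gap of 5 to 10 mmHg. The direction is open: losing large responders would understate the effect, while losing poor tolerators could move it either way.

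A reader might infer more than the documents support:
- That no outcome exists for anyone who stops. A period-2 stop already has a week-8 value.
- That the largest responders are removed. The trigger needs more than 40 mmHg and symptoms together; large falls without symptoms stay in, and on the plan's own SD and correlation the trigger would be rare.
- That the bias could reach 3.0 mmHg. This needs all of the 15% drop-out to be selective product stops and a gap of 20 mmHg (0.15 × 20). Section 2.6 gives no ground for either.
- That keeping these patients would raise power. That holds only if they retain most of the effect while off product.

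The case rests on avoiding outcome-dependent missing data and keeping the scheduled safety observation.

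**What to change.** Leave the stopping criteria, and any decision about further product exposure, to the sponsor. Add to Section 4.2 that a patient who stops the product without withdrawing consent is asked to attend the remaining scheduled visits, at least the one closing the current period, for 24-hour blood pressure and the scheduled safety assessments. Record the date and reason for each stop, by treatment and period.

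In Section 5, keep the completers analysis for the efficacy question. Beside it, report the same mixed model in all randomised patients, using every available period value, including the week-8 values of patients who stop in period 2. A patient with only one period measured adds little within-patient information, so attendance through week 20 is worth asking for.

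The cost is a short amendment and a few attendances at visits already in the schedule. The drawback is that off-product values may dilute the all-randomised estimate, by an amount that the documents do not allow to be computed. The two analyses should therefore be labelled as answering different questions.

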4.3 Potential risks within the study design

All clinical assessments in this trial are standard methods and well established within the Department of Cardiology (MedUniGraz) and its clinical trial section. Thus, the applicant does not expect any methodological risk with respect to the trial. The recruitment of patients into this clinical trial will be based on the cooperation between the applicant and the herz.leben project, in which 120 highly motivated patients per year have been prospectively enrolled since 2007. Therefore, we do not anticipate having problems with recruiting 42 patients from this educational program within 12 months and expect these patients to fully adhere to the study protocol.

Saliva collection by swabbing is a very convenient and non-invasive method for collecting cells in clinical practice. However, saliva samples might not contain enough cells to perform all analyses, including the assessment of autophagic activities. Therefore, whole blood and blood cells (e.g. PBMCs) will be used to detect differences in autophagy, immune cell, and polyamine metabolite profiles. We work under the hypothesis that spermidine induces autophagy in hypertensive patients. If we fail to detect increased autophagy markers upon spermidine supplement, we will use

our data on plasma metabolites (such as L-arginine) and any detected changes in circulatory cell profiles to propose an alternative mode of action (potentially autophagy-independent). If spermidine levels are not increased in whole blood or plasma, our efforts will concentrate on the detection of spermidine-induced changes in polyamine metabolism by analyzing metabolites (i.e. precursors and derivatives of spermidine) in human plasma samples. Moreover, saliva samples offer an additional “tissue”-like sample that will prove the bioavailability of spermidine originating from the administered supplements.

5 Statistical considerations and data analysis

Obtaining repeated measurements from the same patients in response to both treatments has fundamental physiological reasoning (see 3.1) and necessitates completing the study protocol. For this reason and because the trial is designed to measure the treatment efficacy, rather than adherence, patients who drop out before completing the protocol (4 visits) or their baseline treatment regimen changes due to medical reasons will be excluded to maintain a balanced crossover analysis of this trial.

The effect of distinct treatments (spermidine or placebo) on a given parameter (e.g. SBP) will be expressed as a change score from baseline (Δ). The difference between treatment effects will then be evaluated using a mixed linear model, where *Subjects* will be included as a random factor, whereas Treatment (spermidine vs. placebo), *Period* (first vs. second), and *Sequence* (spermidine-placebo vs. placebo-spermidine) will be fixed factors (i.e. predictors). Although we expect no carryover effects due to the washout period, including *Period* and *Sequence* in the model will help exclude any confounding effects of (or interaction with) these aspects, especially taking into account that the obtained data will be well-balanced due to the (2x2) study design.

6 Ethical considerations and informed consent

The study shall be conducted in accordance with the ethical principles originating from the *Declaration of Helsinki*²³ and in accordance with *ICH-Good Clinical Practice* (GCP) and applicable regulatory requirements. The study is registered at the local ethics committee with the number 30-468 ex 17/18.

Before randomisation, patients will be comprehensively informed about spermidine and its effects as a compound and the procedures within the trial, but they will be blinded to the treatment sequence (spermidine vs. placebo). Participants will be given the informed consent form and given enough time to consider voluntary participation.

7 Data collection and quality assurance, Data management, Monitoring

A unique ID number will be attributed to every enrolled patient. Patients' names will be protected and accessible only to the personnel/the applicant involved in the study. Blood/serum samples will be stored in an anonymous fashion and biologically destroyed 5 years after completion of the study.

On-site monitoring will be conducted by the KKS (Koordinierungszentrum für Klinische Studien), MedUniGraz. Accuracy and completeness of the CRF entries, source documents, and other study-related documents will be checked. After each monitoring visit, a report of any significant findings/facts, deviations, and deficiencies will be communicated to the investigator.

Conflict of interest:

[name] and [name] declare a potential financial conflict of interest (equity in TLL). They will not analyze any clinical data and will be blinded throughout the lab analysis after the trial.

